Data Analysis: We will obtain descriptive information on primary and secondary outcomes. In particular, at each time-point, we will obtain the mean, median, SD, and range for each measure and for the changes from baseline for each measure, for the MitoQ and placebo subject groups. We will also obtain 95% confidence intervals for the changes from baseline for each measure, at each time point for both subject groups. We will conduct a t-test to compare primary and secondary measures (changes from baseline) and to obtain the associated 95% confidence intervals for the differences in mean change between the MitoQ and placebo subject groups. We will focus on the confidence intervals that describe the plausible differences in mean change between the subject groups. These confidence intervals will provide information about the magnitude of differences in MFIS and FSS changes between subject groups that are consistent with the previous data. We will also test for differences in the change scores by group in a linear regression framework, adjusting for demographic and clinical characteristics, such as gender. As a secondary analysis, we will use an ANCOVA test with 12-week MFIS score as the outcome and baseline MFIS score as a covariate to account for baseline differences in fatigue among patients. We will use a linear mixed model to analyze MFIS changes over time with fixed effects for time, incorporating baseline values of the outcome as a covariate, and random intercepts and slopes for individuals to incorporate within-subject variability. Due to the exploratory nature of this study, the 6 week time point will provide evidence of whether or not change is seen by 6 weeks. It will allow us to understand how long MitoQ takes to have an effect, and this information will be useful for planning future studies. Both formal hypothesis testing and confidence interval estimation will be conducted. To detect a trend in the effect of MitoQ dosage, we will perform an ANOVA trend analysis on the change in MFIS between baseline and 12 weeks among the three treatment groups. In addition, we will categorize participants who improved by a reliable change, defined as differences in group means divided by the standard error, greater than 1.96 points and test for differences in the proportion of improvers by group using a chi-squared test. The standard error is given by $s_1\sqrt{1 - r_{xx}}$, where s_1 is the standard deviation of the control group and r_{xx} is the MFIS test-retest reliability (here, given by the MFIS Cronbach's alpha value of 0.81.⁶ This analysis will yield additional power (compared to a 2-sample t-test) and will provide useful data for planning a repeated measures analysis in a future larger trial. Secondary outcomes will be analyzed in the same manner. To test if the effect of MitoQ on FSS depended on compliance, compliance (as measured by pill counting) will be treated as a co-variate in the analyses. Patterns of missing data will be examined to determine if patient characteristics are related to missing follow-up data. Statistical significance is defined as $P < 0.05$. SPSS for Windows Version 15.0 (SPSS Inc., Chicago) and SAS (SAS Institute, Cary, NC) will be used for analysis.

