
Anticipated results: We expect that MS veterans taking MitoQ for 12 weeks will have less fatigue than those Veterans with MS taking placebo as determined by the MFIS.

Specific Aim 2: Determine whether Veterans with MS who receive oral MitoQ in comparison to those who receive placebo have improved cognitive function, quality of life and depression using Symbol Digit Modality Test (SDMT), MS Impact Scale -29 (MSIS-29) and the Beck Depression Inventory–Fast Screen scores respectively. Our hypothesis is that by improving mitochondrial function in sub optimally functioning neurons and axons, MitoQ, an efficient mitochondrial targeted therapy, may lead to cognition, quality of life and depression improvement in Veterans with MS.

Introduction: In addition to fatigue, cognitive impairment, poor quality of life and depression are some aspects of MS that have significant adverse impact on patient's lives and not addressed by current treatment options including the disease modifying therapies. Mitochondrial targeted therapy CoQ10 has shown significant improvement in depression (BDI) and quality of life in a small pilot study as compared to placebo.⁴⁶ Since MitoQ is considered to have better mitochondrial penetration than CoQ10, it is worthy of exploring its effects on these poorly managed MS symptoms.

Procedures: At baseline assessment and visits 3 and 4 (6 and 12-week post treatment initiation assessment). At each of these visits, we will also acquire data on each subject's cognitive function using SDMT, quality of life assessment using MSIS-29 and depression using BDI-FS scores.

Statistical Analysis: Exploratory analyses similar to the primary analysis including mixed model that will account for repeated measures will be conducted using the SDMT, MSIS-29 and BDI-FS as the secondary outcome measures. To test if the effect of MitoQ depended on changes in depression a similar model will be constructed including both the baseline and the end of the period BDI-FS. The effect of MitoQ on depression will be evaluated by fitting a model with BDI-FS at the end of each period as the outcome. Baseline values for the SDMT, MSIS-

29, BDI-FS and FSS will be included as covariates, and patient effects treated as random. Changes in activity over time will be analyzed in an exploratory manner using graphical techniques.

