Anticipated results: We expect that MS veterans taking MitoQ will have better cognition and quality of life and less depression than those Veterans with MS taking placebo as determined by the standard measures.

Specific Aim 3: Determine the safety and tolerability of MitoQ in subjects with MS using side effects and blood tests.

Introduction: Results from clinical trials in Hepatitis C and PD as described in the “current status of the field section” suggested that MitoQ is generally well-tolerated and no safety concerns surfaced. To assess the safety and tolerability of oral MitoQ versus a placebo, all subjects (treatment as well as the placebo groups) will undergo monitoring for AEs and side-effects as described below. An adverse event is any untoward medical occurrence (signs, symptoms, intercurrent illness or abnormal lab findings) that occurs in a study subject during the treatment or cross over periods, regardless of suspected cause.

Statistical Analysis: To evaluate patient safety, laboratory test results at baseline and changes from baseline at 6 and 12 weeks will be determined and summarized for each subject group, and will be compared using t-tests for continuous measures and Fisher’s exact test for proportions.

Anticipated results: We expect that MS veterans taking MitoQ will have no significant and unexpected AE on their blood tests and body systems than those Veterans with MS taking placebo.

Specific Aim 4: Determine whether plasma MitoQ levels in Veterans with MS treated with MitoQ correlate with clinical outcomes of fatigue, cognitive function, quality of life, depression, blood inflammatory immune markers, and markers of oxidative stress. We will test the hypothesis that plasma concentrations of MitoQ correlate with fatigue, cognitive function, quality of life and depression in subjects with MS receiving MitoQ compared with those receiving placebo. Additionally, this aim will test the hypothesis that MitoQ will lower the blood concentration of inflammatory immune markers and markers of oxidative stress. We hypothesize that MS subjects receiving MitoQ will have improved levels of blood biomarkers of oxidative stress as seen by lower lipid peroxidation (LPO) products, nitric oxide catabolites (NOC) and superoxide dismutase (SOD) activity and improved TAC.

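### The plan asks whether the MitoQ effect on FSS depends on compliance, but entering compliance as a covariate cannot show it; a treatment-by-compliance term is needed

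*Combined protocol and SAP*

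**What the plan says.** The fatigue analyses are in the combined protocol and SAP, Specific Aim 1, Statistical Analysis (Data Analysis). The basic comparison reads "We will conduct a t-test to compare primary and secondary measures (changes from baseline", with confidence intervals for "differences in mean change between the MitoQ and placebo subject groups". The same paragraph adds a linear regression adjusted for demographic and clinical characteristics, an ANCOVA on baseline, a linear mixed model with random intercepts and slopes, and "an ANOVA trend analysis on the change in MFIS between baseline and 12 weeks among the three treatment groups". Secondary outcomes, which include FSS at 6 and 12 weeks, are to be handled in the same way.

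Compliance has one sentence: "To test if the effect of MitoQ on FSS depended on compliance, compliance (as measured by pill counting) will be treated as a co-variate". No section names a treatment-by-compliance term, an analysis by compliance stratum or any other method for effect modification. The plan does not say how the pill count is coded, whether it is taken in all arms, or whether the two doses are pooled for this test.

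**The concern.** The sentence pairs a question with a method that does not address it. Whether an effect depends on compliance is a question about how the difference between arms changes as compliance changes. Adjusting for compliance holds that difference constant.

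An analyst who follows the text will have one compliance result to report, the covariate's P value, in a plan that tests formally at P < 0.05. If it is significant, the natural but wrong reading is that MitoQ works better in those who take it. If it is not, the wrong reading is that compliance makes no difference to the effect. The pilot is meant to inform later trials, so either misreading could be carried forward.

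**Working it through.** **Inputs.** From the documents: three arms (20 mg, 40 mg, placebo), FSS change as the outcome, pill-count compliance, significance at P < 0.05. The documents give no sample size, allocation ratio, slopes or SD for this analysis, so there is no figure to reproduce. All rates below rest on assumptions; the algebra does not.

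**Algebra.** Let T = 1 for MitoQ and 0 for placebo, and let C be compliance.

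- Covariate model: E[Y] = b0 + b1·T + b2·C. The treatment effect is b1 at every C. If the doses enter separately there are two such effects, each still constant in C.
- Interaction model: E[Y] = b0 + b1·T + b2·C + b3·T·C. The treatment effect is b1 + b3·C, and dependence is b3 ≠ 0.

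If the truth has b3 ≠ 0 but the covariate model is fitted, and compliance has the same distribution in each arm, the compliance coefficient estimates b2 + p·b3, where p is the proportion on MitoQ. This one number mixes the prognostic slope with the dependence and cannot be separated into the two.

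Comparing the treatment coefficient with and without the covariate does not help either. That shift equals the compliance slope times the difference in mean compliance between arms, so it reflects imbalance, not dependence.

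**Simulation 1.** Assumed: equal three-arm allocation with the doses pooled (p = 2/3), standardised skewed compliance, residual SD 1, treatment effect -0.5 SD, 2,000 trials per cell. Rates are for n = 10 / 20 / 50 per arm.

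| Setting | b2 + (2/3)·b3 | Covariate significant | Interaction significant |
|---|---|---|---|
| A. No dependence: b2 = -0.5, b3 = 0 | -0.50 | 71.8 / 95.7 / 100% | 4.8 / 5.6 / 4.7% |
| B. Dependence: b2 = 0, b3 = -0.5 | -0.33 | 38.6 / 66.9 / 96.2% | 20.8 / 41.3 / 81.5% |
| C. Dependence: b2 = +0.4, b3 = -0.6 | 0.4 - 0.4 = 0 | 6.5 / 5.8 / 7.3% | 26.6 / 53.6 / 91.1% |

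A and C show the two errors: the covariate test is usually significant where there is no dependence, and close to its 5% level where dependence is real.

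**Simulation 2.** Assumed: 2:1 allocation, standard normal compliance, residual SD 1, treatment effect -0.5, 20,000 trials per cell. Rates are for total N = 30 / 60 / 90.

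| Slope on MitoQ / placebo | Dependence | Covariate significant | Interaction significant |
|---|---|---|---|
| 0 / 0 | no | 4.8 / 5.0 / 5.0% | 4.8 / 4.9 / 5.1% |
| -0.2 / -0.2 | no | 17.6 / 31.9 / 45.8% | 5.0 / 4.9 / 5.0% |
| -0.3 / -0.3 | no | 33.9 / 60.8 / 78.5% | 5.1 / 4.9 / 4.9% |
| -0.3 / 0 | yes | 17.8 / 31.7 / 44.7% | 10.7 / 17.7 / 24.5% |

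The interaction test keeps its 5% level in all three settings without dependence. The covariate test does so only when compliance is unrelated to outcome.

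**Precision of the interaction.** For slopes -0.3 / 0, the median 95% CI half-width is 0.867, 0.571 and 0.456 SD at N = 30, 60 and 90, against a true difference of 0.3. Large-sample check at N = 90 (60 MitoQ, 30 placebo): SE = √(1/60 + 1/30) = √0.05 = 0.224, and 1.96 × 0.224 = 0.44, close to the simulated value.

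**The case against.** **The wording may be loose.** The stated purpose is dependence, so the authors may have meant an interaction. That is possible, and the text does not rule one out. But none is written, and an analyst working from the text would fit the additive model. If an interaction was intended, the correction is a few words.

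**The stakes are low and the repair is weak.** This is one sentence about a secondary outcome in a self-described exploratory pilot, and the interaction has little power. All of that stands. It argues for reporting an interval without a verdict, not for testing a different quantity.

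**Aim 4 already looks at exposure and response.** It plans to relate plasma MitoQ to clinical outcomes, including fatigue. That is related work but not a substitute. A level drawn an hour after a dose is not a pill count over the treatment period, and the statistical text of that aim deals mainly with biomarkers.

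**The rates are illustrative.** This is correct; they depend on assumed slopes, allocation and compliance distributions. The model-form argument does not.

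**A reader might infer that the covariate test gives the same answer whether or not dependence exists.** That is too strong. Rates match only when the slopes have the same weighted average, as with -0.2 / -0.2 and -0.3 / 0. Elsewhere they differ: at N = 30, the settings without dependence run from 4.8% to 33.9%, against 17.8% with it. The supportable claim is that the test does not identify dependence.

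**A reader might extend the fault to Specific Aim 2**, where the plan writes "To test if the effect of MitoQ depended on changes in depression" and then "a similar model will be constructed including both the baseline and the end of the period BDI-FS". The documents do not support that as an error. The wording may mean mediation, for which such a model is relevant, and models without end-of-period BDI-FS are already planned.

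**Conclusion.** The point holds for the FSS compliance analysis. Followed as written, the plan cannot answer its own question, because its model contains no term for dependence. This rests on the model form and on the absence of an interaction anywhere in the documents, not on any assumed figure. The simulations show only that both kinds of misreading can be frequent in plausible settings.

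A reader might infer that the fatigue results themselves are compromised. They are not. The primary MFIS comparison does not involve compliance, and the planned t-tests and intervals for FSS change stand without it. The defect is confined to one ancillary analysis and is worth correcting before the data are analysed.

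**What to change.** 1. Replace the covariate-only test with a treatment-by-compliance interaction in the FSS change model, using pill counts from all arms, and define how compliance is coded.
2. State how the doses enter. One option is pooled MitoQ against placebo, to match the t-test, with dose-specific slopes shown descriptively. Pooling assumes one compliance slope for both doses, which sits uneasily with the planned dose-trend analysis, so the choice should be explicit.
3. Report the interaction estimate with its 95% CI. Label it exploratory: compliance arises after randomisation and is self-selected, so even the correct term is not a randomised contrast.
4. Keep the FSS treatment effect from the model without compliance. The planned t-tests largely do this already; one sentence would settle it.

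The cost is a short wording change and one model term. No new measurement is needed if pill counts cover all arms, which should be confirmed. The downside is the imprecision shown above, so a wide interval should not be read as evidence that compliance does not matter.

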MitoQ for Fatigue in Multiple
Sclerosis: A Placebo Controlled Trial

NCT04267926

September 23, 2021

Title

MitoQ for fatigue in multiple sclerosis: a placebo-controlled trial

Specific Aims/Purpose

Specific Aim 1: Determine whether Veteran's with MS (VwMS) who receive oral MitoQ in comparison to those who receive placebo have less fatigue after a 12-week treatment period as measured by MFIS Score.

Specific Aim 2: Determine whether VwMS who receive oral MitoQ in comparison to those who receive placebo have improved cognitive function, quality of life and depression using Symbol Digit Modality Test (SDMT), MS Impact Scale -29 (MSIS-29) and the Beck Depression Inventory–Fast Screen scores respectively.

Specific Aim 3: Determine the safety and tolerability of MitoQ in VwMS using side effects and blood tests.

Specific Aim 4: Determine whether plasma MitoQ levels in VwMS treated with MitoQ correlate with clinical outcomes of fatigue, cognitive function, quality of life and depression and with blood based inflammatory immune and oxidative stress biomarkers.

The proposed work is innovative; the

Hypothesis: The central hypothesis is that oral MitoQ with its mitochondrial affinity will improve MS related fatigue, cognition, quality of life and mood by improving mitochondrial function and resultant neuronal energy depletion in neurons.

Research Design and Methods

We propose to conduct a double-blind, placebo-controlled, pilot trial to compare the administration of a 20 and 40 mg dose of oral MitoQ to a placebo, as a treatment to reduce fatigue in MS subjects. There is no research to guide the study supplement dosage for this study. We have chosen 20 and 40 mg dosages based on correspondence from the manufacturer as noted above, in addition to the published recommendation in an article reviewing all the human and animal studies on MitoQ. The participation period for each subject will be 13 weeks: screening visit during the first week, followed by a 12-week treatment period. The study will require 4 visits and 4 phone calls over 13 weeks. Total time commitment is approximately 7 hours.

Overall Design

Aims	Outcomes	Description

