1. Determine whether Veterans with MS who receive oral MitoQ in comparison to those who receive placebo have less fatigue after a 12-week treatment period as measured by MFIS Score.	Primary Outcome: MFIS Secondary Outcome: FSS	Double-Blind, randomized groups assigned to either 20 or 40 mg of MitoQ or an identical placebo. Check MFIS, and FSS and SDMT at time 0, 6 and 12 wks
2. Determine whether Veterans with MS who receive oral MitoQ in comparison to those who receive placebo, have improved cognitive function, quality of life and depression using SDMT, MSIS-29 and the BDI–FS scores respectively.	Secondary Outcome: SA-EDSS and BDI.	Double-Blind, randomized groups assigned to either 20 or 40 mg of MitoQ or an identical placebo. Check SA-EDSS and BDI at time 0 and 12 weeks
3. Determine the safety and tolerability of MitoQ in subjects with MS using side effects and blood tests.	Secondary Outcome: Safety.	Monitoring of patient response and reporting/recording AEs
4. Determine whether plasma MitoQ levels in Veterans with MS treated with MitoQ correlate with clinical outcomes of fatigue, cognitive function, quality of life, depression, blood inflammatory immune markers, and markers of oxidative stress.	Secondary Outcome: Plasma levels of oral MitoQ 1 hr post-drug. Plasma and/or PBMC IFN- γ , TNF- α , IL-2, IL-6 and IL-17, MDA, HAE, TAC, NOC and SOD	Data collection on MitoQ plasma levels and inflammatory and oxidative stress markers at baseline, week 6 and 12.

Subject Visits and Assessment Schedule

Table 2. Study Activities

	Week 0	Week 1	Week 7	Week 13	
	Visit 1	Visit 2	Visit 3	Visit 4	
Visit time	2 hours	2.5 hours	2.5 hours	2.5 hours	
Purpose	screen, consent	begin treatment	in clinic follow up	end treatment	Total blood draw amount
Consent	X				
Vital signs	X	X	X	X	
Medical history, physical neurological exam	X			X	
T25W, 9HPT, SDMT		X	X	X	
BDI, FSS, MFIS, MSIS-29	X	X	X	X	
Blood testing CBC w/ diff (4mls) CMP (6mls)	X		X	X	30 mls
Blood draw for plasma MitoQ level (4mls)		X	X	X	12 mls
Blood draw for Inflammatory immune markers 40 mls		X	X	X	120 mls
Medication reconciliation	X	X	X	X	
Urine testing (female)	X		X	X	
Side effect monitoring			X	X	

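### The exploratory Aim 2 check on whether the MitoQ effect depends on depression adjusts for end-of-treatment BDI-FS, itself an outcome, and so can test neither mediation nor moderation

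*Combined protocol and SAP*

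**What the plan says.** The Statistical Analysis paragraph of Specific Aim 2 plans exploratory analyses, including a "mixed model that will account for repeated measures will be conducted using the SDMT, MSIS-29 and BDI-FS as the secondary outcome measures". It then adds a model to find out whether the MitoQ effect "depended on changes in depression a similar model will be constructed including both the baseline and the end of the period BDI-FS". That sentence names no outcome, interaction, indirect effect or comparison with a model lacking follow-up BDI-FS. It does not define the period either; I take its end to be the 12-week visit.

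The plan treats the same variable as something MitoQ acts on:

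- The next sentence reads: "The effect of MitoQ on depression will be evaluated by fitting a model with BDI-FS at the end of each period as the outcome".
- The Aim 2 hypothesis is that MitoQ "may lead to cognition, quality of life and depression improvement in Veterans with MS".
- The central hypothesis is that oral MitoQ "will improve MS related fatigue, cognition, quality of life and mood by improving mitochondrial function".

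On timing, Table 2 puts "BDI, FSS, MFIS, MSIS-29" in one row, ticked at all four visits, and the Aim 2 Procedures collect BDI-FS at baseline, 6 and 12 weeks. The Aim 2 row of the Overall Design table instead says "Check SA-EDSS and BDI at time 0 and 12 weeks". I assume that BDI in the two tables means the BDI-FS.

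**The concern.** A covariate that treatment can change is not a neutral adjustment. Once end-of-period BDI-FS is in the model, the arm coefficient compares patients with equal depression scores at the end of treatment. If MitoQ improves mood, such patients are no longer a randomised comparison.

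The natural reading of the output would be that a shrinking MitoQ coefficient shows dependence on depression. Yet the coefficient also shrinks when fatigue drives mood, and when one mechanism improves both. The second is close to the trial's own central hypothesis. The two scales come from one visit, so the model has no time order with which to tell these explanations apart. If dependence means instead that MitoQ works better in some patients than in others, a main-effect covariate cannot show it.

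The pilot is meant to inform later trials, so a misread pathway could be carried into their design.

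**Working it through.** The documents give no effect size, SD or correlation for these scales, so there is no planned figure to reproduce. All values below are assumptions. Effects are in within-arm SD units (given baseline), and every scale is oriented so that a positive effect is a benefit.

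**1. What the adjusted coefficient estimates.** Let d_out be the total MitoQ effect on the outcome, d_BDI its effect on end-of-period BDI-FS, and r their within-arm correlation. Least squares gives

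adjusted arm coefficient = d_out − r × d_BDI.

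**2. Range of the shift.**

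| d_out | d_BDI | r = 0.3 | r = 0.5 | r = 0.7 |
|---|---|---|---|---|
| 0.4 | 0.4 | 0.28 | 0.20 | 0.12 |
| 0.5 | 0 | 0.50 | 0.50 | 0.50 |
| 0.5 | 0.2 | 0.44 | 0.40 | 0.36 |
| 0.5 | 0.3 | 0.41 | 0.35 | 0.29 |
| 0.5 | 0.5 | 0.35 | 0.25 | 0.15 |
| 0 | 0.4 | −0.12 | −0.20 | −0.28 |

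Example from the first row: 0.4 − 0.5 × 0.4 = 0.20. With equal effects the loss is 30% to 70%. With d_BDI at 0.2 or 0.3 against 0.5 it is 12% to 42%. With d_BDI = 0 it is nil. In the last row MitoQ helps mood only, and the model shows an apparent worsening of the other outcome.

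**3. Does shrinkage identify mediation?** Take three mechanisms, each with a total effect of 0.30 on 12-week fatigue. With b the within-arm slope of fatigue on week-12 BDI-FS, the adjusted coefficient is 0.30 − b × (effect on BDI-FS).

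- *Full mediation* (fatigue = 0.5 × BDI-FS + noise; effect on BDI-FS 0.60): 0.30 − 0.50 × 0.60 = 0.00.
- *Reverse causation* (BDI-FS = 0.5 × fatigue + noise of SD 0.87; fatigue variance 0.98; effect on BDI-FS 0.15): b = 0.49 / (0.25 × 0.98 + 0.757) = 0.49, so 0.30 − 0.49 × 0.15 = 0.23.
- *Shared cause* (both scales load 0.7 on one unmeasured factor, noise SD 0.7; effect on BDI-FS 0.30): b = 0.49 / 0.98 = 0.50, so 0.30 − 0.50 × 0.30 = 0.15.

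Large simulations (1,000,000 patients per mechanism) agreed to within 0.01. The coefficient shrinks in all three, although depression carries the effect only in the first.

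**4. Would week-6 BDI-FS help?** The coefficient of week-6 BDI-FS on 12-week fatigue, with arm in the model, was:

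| Mechanism | Without week-6 MFIS | With week-6 MFIS |
|---|---|---|
| Full mediation | 0.35 | 0.35 |
| Reverse causation | 0.35 | 0.00 |
| Shared cause | 0.50 | 0.33 |

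Without the week-6 outcome, the same-visit problem only moves from week 12 to week 6. With it, reverse causation is separated from mediation, but a shared cause is not. Nor should the arm coefficient in this model be read as a treatment effect: with both week-6 scores included it falls from 0.30 to 0.09 under reverse causation, where depression carries nothing.

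**The case against.** Several points on the other side stand.

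- *The primary result is untouched.* The Aim 1 t-test, the ANCOVA and the MFIS mixed model do not list end-of-period BDI-FS. A reader might infer that the trial's estimate of the MitoQ effect on fatigue is distorted; the documents do not support that. The model at issue also sits among analyses labelled exploratory.
- *Week-6 BDI-FS is not wasted.* A reader might infer that it is collected and never used. It can enter the repeated-measures model with BDI-FS as outcome, and is absent only from the depression-dependence model.
- *Removing the part associated with depression is what a direct-effect model does.* True, so a lower coefficient is not an error in itself. But a direct-effect reading needs a planned contrast with the total effect and an assumption of no mediator-outcome confounding, and neither is stated.
- *Mediation is one reading only.* The Aim 1 analysis uses the same expression of dependence for compliance, which suggests effect modification. That does not rescue the model, since modification needs an interaction and none is given.
- *The outcome may not be fatigue.* The sentence follows one about SDMT, MSIS-29 and BDI-FS. The algebra holds for SDMT or MSIS-29 too, and with BDI-FS as outcome the model would be circular.

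**Conclusion.** The point holds for this one exploratory model. As written, it conditions on a concurrent post-randomisation outcome and contains nothing that would test mediation or moderation, so its MitoQ coefficient is neither a treatment effect nor evidence about depression.

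The size is conditional. The coefficient moves by r × d_BDI: nothing if MitoQ leaves BDI-FS unchanged or BDI-FS is uncorrelated with the outcome, 12% to 42% of an assumed 0.5 SD effect at modest BDI-FS effects, and 30% to 70% if both scales benefit equally. It would go too far to say that the model necessarily removes real effect, or to treat any of these percentages as a forecast for this trial.

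The plan should be changed because the fix is nearly free, but no primary conclusion depends on it. The conflict over whether BDI is taken at 6 weeks is a separate documentation matter. It bears on this point only because a mediation analysis would need the 6-week value.

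**What to change.** 1. Estimate the MitoQ effect from models with baseline BDI-FS only; the plan already lists it as a covariate. State that a coefficient adjusted for end-of-period BDI-FS will not be read as a treatment effect or as dependence on depression.
2. Name the outcome, define the period, and say whether moderation or mediation is meant.
3. If moderation: test the treatment by baseline BDI-FS interaction.
4. If mediation: pre-specify an analysis, labelled exploratory, with week-6 BDI-FS as mediator of the 12-week outcome, adjusted for baseline BDI-FS and for the baseline and week-6 values of that outcome. Report the indirect effect with its confidence interval instead of inferring it from shrinkage of the arm coefficient. Add a sensitivity analysis for mediator-outcome confounding, which week-6 data do not remove.
5. Reconcile the BDI timing in the Aim 2 row of the Overall Design table with Table 2 and the Aim 2 Procedures.

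The cost is analysis wording and one table cell, with no assessment beyond those in Table 2. The downsides are that a week-6 mediator misses mood change between weeks 6 and 12 (in the full-mediation example, 0.30 − 0.60 × 0.35 = 0.09 of the effect is not attributed to it), and that the indirect effect will be imprecise in a pilot.
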